## 2.7.3 Laboratory data

Fasting glucose parameter, when used in any analysis, will require the lab sample to be taken while fasting. Glucose values recorded at non-fasting state will not be used.

### 2.7.3.1 Summary tables using descriptive statistics

Summaries for safety laboratory values will include observed value, changes and percent changes from ORION-8 baseline over time:

- Hematology and coagulation parameters will be summarized at ORION-8 baseline (for observed value only), at Day 1080, and at EOS.
- Safety chemistry parameters in the full serum chemistry panel but not in limited serum chemistry panel will be summarized at ORION-8 baseline (for observed value only), at Day 1080, and at EOS.
  - These include direct and indirect bilirubin, lactate, bicarbonate, uric acid, urea (blood urea nitrogen; BUN), sodium, potassium, calcium, inorganic phosphorus, chloride, albumin, total protein, fasting glucose.
- Safety chemistry parameters in limited chemistry panel, which is a subset of the full chemistry panel, will be summarized at ORION-8 baseline (for observed value only), at each scheduled visit from Day 90 to Day 1080, and at EOS.
  - These include aspartate aminotransferase (AST), alanine aminotransferase (ALT), alkaline phosphatase (ALP), gamma glutamyl transferase (GGT), total bilirubin (TBIL), creatine kinase (CK), creatinine, eGFR, glycated hemoglobin A1C (HbA1c).

### 2.7.3.2 Shift analysis

A shift analysis from baseline to EOS will be performed for eGFR and HbA1c using the following categories:

- For eGFR, the categories will be Severe =  $< 30$  mL/min/1.73m^2; Moderate =  $\geq 30$  to  $< 60$  mL/min/1.73m^2; Mild =  $\geq 60$  to  $< 90$  mL/min/1.73m^2; and Normal =  $\geq 90$  mL/min/1.73m^2.
- For HbA1c, the categories will be  $< 5.7\%$ ,  $\geq 5.7\%$  to  $< 6.5\%$ , and  $\geq 6.5\%$ .

### 2.7.3.3 Clinically significant laboratory values

The number and percentage of subjects with potentially clinically significant (PCS) laboratory values or clinically significant (CS) laboratory values (refer to [Appendix 5.3](#) for the criteria) will be summarized. For AST, ALT and CK, the most severe result for each subject will be used. For creatinine, the following two categories will also be presented in addition to the CS criterion:

- 1) Subjects with the baseline value  $\leq 2$  mg/dL and any post-baseline value  $> 2$  mg/dL.
- 2) Subjects who are not in the first category but has  $\geq 50\%$  increase from baseline.

For liver chemistry parameters (ALT, AST, ALP, TBIL), the number and percentage of subjects whose PCS/CS value returned to baseline level at the last measurement will also be summarized. Here the baseline level is defined as a value of the same category as the baseline category or a value of a better category than the baseline. For example, if a subject's baseline ALT is  $>3$  and  $\leq 5$  x ULN and the subject's ALT elevated to  $>5$  and  $\leq 10$  x ULN at the worst measurement post baseline, the subject is considered to have returned to baseline level at the last measurement if the last ALT value of that subject is  $\leq 5$  x ULN.

Listings of all subjects with PCS or CS laboratory values will be presented. Subjects will appear once per lab parameter but may appear under multiple lab parameters.

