10.3.4.2 Laboratory Tests

Laboratory values will be summarized at each time point. Analyses will also be performed for each lab parameter for incidence rates of potentially clinically significant (PCS) values for subjects without PCS value at baseline (defined as baseline in the corresponding Phase II or Phase III feeder study), as well as without PCS value at Day 1 of the study

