### 2.1 Data analysis general information

All analyses will be performed by Novartis, [REDACTED]. [REDACTED] The most recent version of SAS available in the statistical programming environment of Novartis will be used for the analysis.

Study-collected data will be summarized by the actual treatment groups of the feeder studies (Phase III Inclisiran-Inclisiran, Phase III Placebo-Inclisiran, ORION-3 Rollover) using descriptive statistics, graphs, and/or raw data listings. Categorical variables will be summarized using counts and percentages. Percentages are based on the number of subjects in the analysis set for whom there are non-missing data, unless otherwise specified. For selected categorical variables, the 95% confidence interval (CI) for the percentage will be calculated using Blaker's method. Continuous variables, including changes from baseline, will be summarized using

descriptive statistics (n (number of non-missing observations), mean, standard deviation (SD), median, first and third quartiles (Q1 and Q3), minimum and maximum). For selected continuous variables, the CI for the mean will be provided.

Absolute change and percent change from baseline will be calculated as follows:

- Absolute change from baseline to Day X = Value at Day X – Baseline value.
- Percent change from baseline to Day X = (Absolute change/Baseline value)\*100%.

For laboratory measurements below the lower limit of quantification (LLQ), LLQ/2 will be used as the numeric value for the measurement. For example, if numeric result is missing in the database and character result is “< 3”, the numeric result should be treated as  $3/2 = 1.5$  during analysis.

Analyses for the final CSR will be conducted after the final database lock (DBL) of the study. The final DBL will be performed after ORION-9/10/11 rollover subjects either complete the Day 1080 visit or discontinue early and will not wait until ORION-3 rollover subjects complete Day 1080 visit. The ORION-3 rollover subjects will have shorter than 3 years of participation in this study, and their EOS visit will be scheduled 90 days after their last dosing visit.

Information regarding DMC analysis will be provided in the DMC charter and a separate DMC SAP/TFL shells.

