## **2.7 Safety analyses**

The safety objectives of this study are to evaluate the safety and tolerability profile of long-term use of inclisiran.

Unless otherwise specified, safety evaluations will be performed for the Safety Population overall and by treatment group of the feeder studies.

Safety analyses are based on observed values and missing data will not be imputed.

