### 2.7.3.4 Hy's law

The number and percentage of subjects satisfying Hy's Law will be tabulated based on the following lab findings:

- Any elevated post-baseline aminotransferases defined as:
  - ALT  $> 3$  x ULN or
  - AST  $> 3$  x ULN
- Elevated post-baseline serum total bilirubin (TBL)  $> 2$  x ULN and serum alkaline phosphatase (ALP) levels  $< 2$  x ULN

Subjects must meet all of the criteria listed above at the same time point and have normal lab parameters (ALT, AST, TBL) at baseline to be considered a Hy's Law case. A second summary will be presented that includes subjects who meet all of the criteria listed above at the same time point without regard to the baseline lab parameter results. The baseline here refers to ORION-8 baseline.

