### 5.3 Criteria for potentially clinically significant and clinically significant abnormal laboratory tests

Hemoglobin A1c criteria is explicitly stated in the table below. For all other parameters, a PCS/CS criterion is met when both of the following occur (baseline refers to ORION-8 baseline):

- There is a post-baseline value that meets the threshold
- The baseline value does not meet the threshold

Some examples are:

- For leukocytes, a subject satisfies “ $\leq 2.8 \times 10^9/L$ ” criterion as long as the baseline value is  $> 2.8 \times 10^9/L$  and any post-baseline value is  $\leq 2.8 \times 10^9/L$ ; a subject satisfies “ $\geq 16 \times 10^9/L$ ” criterion as long as the baseline value is  $< 16 \times 10^9/L$  and any post-baseline value is  $\geq 16 \times 10^9/L$ .
- For CK, a subject satisfies “ $> 3$  and  $\leq 5 \times ULN$ ” criterion as long as the baseline value is  $\leq 3 \times ULN$  and any post-baseline value is  $> 3$  and  $\leq 5 \times ULN$ . A subject satisfies “ $> 5$  and  $\leq 10 \times ULN$ ” criterion as long as the baseline value is  $\leq 5 \times ULN$  and any post-baseline value is  $> 5$  and  $\leq 10 \times ULN$ . If a subject satisfies both “ $> 3$  and  $\leq 5 \times ULN$ ” and “ $> 5$  and  $\leq 10 \times ULN$ ” criteria and does not satisfy the criteria of any more severe category, the subject will be presented under “ $> 5$  and  $\leq 10 \times ULN$ ” but not under “ $> 3$  and  $\leq 5 \times ULN$ ” because the most severe category will be used for CK.
- For serum creatinine, the CS criterion is satisfied if at least one of the following is true:

- The baseline value is  $\leq 2$  mg/dL and any post-baseline value is  $> 2$  mg/dL.
- Any post-baseline value is  $\geq 50\%$  increase from baseline, regardless of whether the baseline value is  $\leq 2$  mg/dL.

Parameter	Unit	Lower Boundary	Upper Boundary
Hematology			
Hematocrit	%	$\leq 0.8 \times \text{LLN}$	N/A
Hemoglobin	g/dL	$\leq 10$ g/dL	N/A
Platelet Count	$10^9/\text{L}$	$\leq 75^*$	$\geq 700^*$
White Blood Cell (Leukocyte) Count	$10^9/\text{L}$	$\leq 2.8$	$\geq 16$
Serum Chemistry			
Alanine Aminotransferase (ALT/SGPT)	U/L	N/A	$> 1$ and $\leq 3 \times \text{ULN}$
Alanine Aminotransferase (ALT/SGPT)	U/L	N/A	$> 3$ and $\leq 5 \times \text{ULN}^*$
Alanine Aminotransferase (ALT/SGPT)	U/L	N/A	$> 5$ and $\leq 10 \times \text{ULN}^*$
Alanine Aminotransferase (ALT/SGPT)	U/L	N/A	$> 10$ and $\leq 20 \times \text{ULN}^*$

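### PCS/CS laboratory percentages: subjects already past a threshold at ORION-8 baseline cannot be cases, yet the SAP's default keeps them in the denominator

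*SAP*

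**What the plan says.** SAP 2.7.3.3 tabulates "The number and percentage of subjects with potentially clinically significant (PCS) laboratory values or clinically significant (CS) laboratory values" and refers to Appendix 5.3 for the criteria. It gives no denominator.

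Appendix 5.3 applies a two-part rule to every parameter except HbA1c. A post-baseline value must meet the threshold, and "The baseline value does not meet the threshold". Baseline here is ORION-8 baseline. The CK example shows how bands work: to count in the band above 3 and up to 5 x ULN, the baseline must be at or below 3 x ULN. There are two exceptions. HbA1c has its own criterion (at least 6.5% together with a change of at least 0.5%). The creatinine limb for a rise of at least 50% applies whatever the baseline level. Appendix 5.3 gives no denominator either.

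The general rule is in SAP 2.1: "Percentages are based on the number of subjects in the analysis set for whom there are non-missing data, unless otherwise specified". SAP 2.7 adds that, by default, "safety evaluations will be performed for the Safety Population overall and by treatment group of the feeder studies".

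Protocol 10.3.4.2 asks for "incidence rates of potentially clinically significant (PCS) values for subjects without PCS value at baseline", meaning feeder-study baseline, "as well as without PCS value at Day 1 of the study". SAP Section 4 records no departure from the protocol's analyses.

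In SAP 2.7.3.4, subjects in the first Hy's law summary must "have normal lab parameters (ALT, AST, TBL) at baseline to be considered a Hy's Law case". The second summary drops that condition.

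**The concern.** An incidence needs the same people eligible for the numerator and the denominator. Here the numerator is restricted to subjects on the normal side of the threshold at baseline, while the default denominator is not. A subject already past the threshold has non-missing data and so is counted in the denominator, but cannot be a case for that threshold. The error runs in one direction only, towards lower percentages.

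Safety is one of the two primary objectives, and these percentages are shown by feeder treatment group. If baseline prevalence differs between groups, the columns are diluted by different amounts. The problem is separate from the choice of baseline visit and would arise with either one.

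**Working it through.** **Inputs**
- Numerator x: subjects who meet the two-part rule (SAP Appendix 5.3).
- Denominator N: subjects in the analysis set with non-missing data (default in SAP 2.1).
- B: subjects in N who already meet the threshold at ORION-8 baseline; b = B/N. The documents do not give b, so the values below are assumptions.
- True at-risk incidence of 20%: an assumption for illustration.
- 2991 enrolled (protocol, rationale for Amendment 2): used only to scale the example.

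The plan states no expected PCS/CS rate, so there is no figure to reproduce.

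**Formula**
- Under the SAP default: x/N.
- Among subjects at risk, as protocol 10.3.4.2 frames it: x/(N - B).
- Ratio: (N - B)/N = 1 - b.

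The ratio does not depend on the event rate. The relative understatement equals b.

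**Numbers, true incidence 20%**
- b = 5%: 20 x 0.95 = 19.0%
- b = 15%: 20 x 0.85 = 17.0%
- b = 25%: 20 x 0.75 = 15.0%

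In counts, with N = 2991 and b = 15%: B = 449, so 2542 are at risk. With 508 cases, 508/2991 = 17.0% and 508/2542 = 20.0%.

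Two columns with the same true 20%, one with b = 5% and the other with b = 15%, would show 19.0% and 17.0%. That two-point gap comes only from the denominator.

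**Where b can be large**
- ALT or AST above 3 x ULN and total bilirubin above 2 x ULN: exclusion criterion 4 (protocol 4.3) bars unexplained elevations of this size at the last feeder visit, so b should be near zero.
- ALT and AST above 1 and up to 3 x ULN: no laboratory limit at entry.
- CK: no entry criterion sets a limit. For its lowest tier, b is the share of subjects with baseline CK above 1 x ULN.
- HbA1c: a subject with baseline at or above 6.5% can still be a case, so the mismatch does not arise.
- Creatinine: the limb for a rise of at least 50% is open to every baseline. Only the limb above 2 mg/dL carries the baseline condition.

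**Is the denominator really the default?** The SAP states its exceptions elsewhere. Baseline categories use all subjects including those with missing values, and child-bearing potential uses females (2.3.2). Injection summaries use doses given or missed (2.4.1). Time to new-onset diabetes is limited to subjects without diabetes at baseline (2.7.4.4). Sections 2.7.3.3 and 5.3 contain no such statement.

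**The case against.** The strongest reply is that the SAP nowhere says that baseline-abnormal subjects stay in the denominator. The default yields where something else is specified, the SAP is built on a protocol that asks for at-risk incidence, and Section 4 declares no change. An at-risk denominator is therefore an available reading. This stands in part: the diluted denominator is inferred from the default, not written. It remains the more literal reading, because the SAP spells out its exceptions elsewhere, and a programmer following the text would use it.

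It is also fair that the analyses are descriptive and noncomparative, that no decision rule uses these percentages, and that case counts and the planned listings do not depend on the denominator. This limits the consequence but does not make the percentage correct.

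Several stronger inferences are tempting, and the documents do not support them:
- *Every PCS/CS percentage is biased low.* HbA1c and the creatinine limb for a rise of at least 50% lie outside the baseline rule.
- *Baseline-abnormal subjects can never be cases.* The bar applies per threshold. A subject at 2 x ULN at baseline can still count in a tier above 3 x ULN.
- *The main liver safety signals are diluted.* Exclusion 4 keeps b near zero for those ALT, AST and bilirubin rows.
- *The Hy's law summary departs from protocol 10.3.4.2.* That section concerns PCS values, not Hy's law. The first summary does have a similar mismatch, but its effect should be small, and the second summary is free of it.

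**Conclusion.** The point holds for the criteria governed by the two-part rule in Appendix 5.3. On the SAP's stated default, the reported percentage is the at-risk incidence times (1 - b). It is not the protocol's quantity, and SAP Section 4 does not say so.

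The direction and the factor are certain if the default denominator is used. The size is not, because b is not in the documents: 19.0, 17.0 or 15.0% instead of 20% rests entirely on assumed b of 5, 15 or 25%. The material effect, if any, should fall mainly on the ALT, AST and CK tiers above 1 and up to 3 x ULN. This should be corrected before the tables are produced, but it does not threaten the trial's conclusions.

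**What to change.** Add one denominator rule to SAP 2.7.3.3 and Appendix 5.3, and show the resulting n in each row:

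- **Criteria under the two-part rule, per parameter and tier:** subjects with a non-missing baseline on the non-abnormal side of that threshold and at least one post-baseline value. For banded tiers this means a baseline at or below the tier's lower bound. Asking only that the baseline lie outside the band would wrongly admit, for example, a baseline CK of 6 x ULN to the row above 3 and up to 5 x ULN.
- **Creatinine above 2 mg/dL category:** subjects with baseline at or below 2 mg/dL and at least one post-baseline value.
- **HbA1c, the creatinine limb for a rise of at least 50%, and the combined creatinine CS criterion:** all subjects with a baseline and at least one post-baseline value. A restricted denominator here would drop subjects who can be cases.
- **Optional, for consistency:** base the first Hy's law summary on subjects with normal baseline ALT, AST and TBL.

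As the SAP uses ORION-8 baseline throughout Appendix 5.3, this rule supplies the Day 1 part of protocol 10.3.4.2. The feeder-baseline part is a separate matter.

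The cost is one rule in the SAP and an n per row, with no new data. Affected percentages rise by the factor 1/(1 - b) and so look somewhat less favourable.

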### 2.7.3.4 Hy's law

The number and percentage of subjects satisfying Hy's Law will be tabulated based on the following lab findings:

- Any elevated post-baseline aminotransferases defined as:
  - ALT  $> 3$  x ULN or
  - AST  $> 3$  x ULN
- Elevated post-baseline serum total bilirubin (TBL)  $> 2$  x ULN and serum alkaline phosphatase (ALP) levels  $< 2$  x ULN

Subjects must meet all of the criteria listed above at the same time point and have normal lab parameters (ALT, AST, TBL) at baseline to be considered a Hy's Law case. A second summary will be presented that includes subjects who meet all of the criteria listed above at the same time point without regard to the baseline lab parameter results. The baseline here refers to ORION-8 baseline.

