4.4.1 Individual Subject Dosing Stopping Criteria

During the study subjects will have clinic visits at regular intervals. Dosing with inclisiran should be temporarily discontinued or stopped in subjects with:

1. Intolerable AEs, or if the investigator believes that continuing dosing will be detrimental to the subject's mental or physical health. This includes severe or serious reactions at the injection site and any anaphylactic type reactions.
2. Unexplained increases in transaminases (ALT or AST) or total bilirubin as follows:
 - a. ALT or AST >8xULN

- b. ALT or AST >5xULN for more than 2 weeks
- c. ALT or AST >3xULN and (total bilirubin >2xULN or INR >1.5)
- d. ALT or AST >3xULN with the appearance of fatigue, nausea, vomiting, right upper quadrant pain or tenderness, fever, rash, and/or eosinophilia (>5%)

The investigator should evaluate to see if other causes for the laboratory abnormalities are immediately apparent, such as obstructive gall bladder or bile duct disease, viral or alcoholic hepatitis, malignancy involving the liver, congestive hepatopathy, other hepatotoxins or heritable disorders.

- 3. Unexplained creatine kinase (CK) values >5 x ULN confirmed by repeat test when the CK elevation is associated with muscle pain, muscle tenderness and/or muscle weakness, or new onset renal dysfunction.

In the case that study medication is permanently discontinued the subject will be asked to return to complete an EOS visit, which should occur at least 90 days following the last dose of inclisiran.

All subjects should be followed until all clinically significant laboratory abnormalities return to normal or to the baseline state. Subjects discontinuing the trial due to withdrawal of consent or initiation of other PSCK9 lipid lowering therapies will not be followed up within the trial.

5 Treatment of Subjects

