5.3 Medical Management Guidelines

5.3.1 Adverse events

Adverse events or abnormal test findings must be followed until the event (or its sequelae) or the abnormal test finding resolves, stabilizes at a level acceptable to the Sponsor/Investigator and/or returns to baseline values.

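### Neither Hy's law summary counts a subject whose ALT and AST are no longer above 3xULN when bilirubin exceeds 2xULN, and no planned output links the two elevations

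*SAP*

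**What the plan says.** SAP 2.7.3.4 sets three laboratory conditions: ALT or AST >3xULN, total bilirubin >2xULN, and ALP <2xULN, all post-baseline. For the first summary, "Subjects must meet all of the criteria listed above at the same time point", and ALT, AST and bilirubin must also have been normal at ORION-8 baseline. The second summary covers "subjects who meet all of the criteria listed above at the same time point without regard to the baseline lab parameter results". Only the baseline condition is dropped; the timing condition stays. The general definitions in SAP 2.1.1 do not say whether a time point is a sample, a date or a visit.

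Protocol Table 6-1 schedules chemistry at Days 90, 270, 450, 630, 810 and 990 and at EOS (Day 1080). ALT, AST, ALP and bilirubin are in both the full and the limited panel (Protocol 7.1.6.3), so each scheduled draw gives all four values. Between visits, Protocol 5.3.1 says: "Adverse events or abnormal test findings must be followed until the event (or its sequelae) or the abnormal test finding resolves". It gives stabilisation and return to baseline as alternative end points, but neither it nor Protocol 4.4.1 sets a retest interval.

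Two other planned outputs bear on the liver. SAP 2.7.3.3 with Appendix 5.3 counts and lists subjects with ALT or AST >3xULN and subjects with bilirubin >2xULN, parameter by parameter, if the ORION-8 baseline value does not already meet the threshold. SAP 2.7.1.1.2 with Appendix 5.2 summarises and lists hepatic adverse events.

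**The concern.** If bilirubin rises after the transaminases, the two elevations may overlap only briefly or not at all. Scheduled draws are months apart, so such a course would be documented mainly by unscheduled follow-up samples on different dates. Stopping criterion 2b in Protocol 4.4.1, which refers to an elevation lasting more than 2 weeks, cannot be judged without such repeat samples. The trial would then hold the sequence of values while the Hy's law count ignored it.

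Safety is a primary objective (Protocol 2.1), hepatic events are an AESI (SAP 2.7.1.1.2), and drug-induced liver injury is a named example of a signal on which the study could be terminated (Protocol 8.6.2). Compared with a rule that allows a time window, the same-time-point rule can only lose cases.

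**Working it through.** The plan states no figure on this point, so there is none to reproduce. Three checks were made.

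**1. The rule on test patterns.** Values are multiples of ULN. ALP is 1.2 to 1.3 throughout and AST is taken as no higher than ALT. The comparison rule accepts bilirubin >2 at the same or a later sample after ALT or AST >3.

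| Pattern | Planned rule | Sequential rule |
|---|---|---|
| ALT 10 with bilirubin 2.5 together | counted | counted |
| ALT 10, bilirubin 1.2; then ALT 5, bilirubin 2.5 | counted | counted |
| ALT 10, bilirubin 1.2; then ALT 2.5, bilirubin 2.5 | not counted | counted |
| ALT 10, bilirubin 1.2; then ALT 3.0, bilirubin 2.5 | not counted | counted |

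Only the last two rows differ. The planned rule needs ALT or AST above 3xULN at the bilirubin time point; it does not need the peak.

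**2. How long a lag the planned rule tolerates.** If ALT falls from a peak P (in multiples of ULN) with halving time h, it stays above 3xULN for h x log2(P/3). The halving time is an assumption.

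| Peak P | log2(P/3) | h = 2 days | h = 7 days | h = 14 days | h = 30 days |
|---|---|---|---|---|---|
| 4 | 0.42 | 0.8 | 2.9 | 5.8 | 12.5 |
| 10 | 1.74 | 3.5 | 12.2 | 24.3 | 52.1 |
| 20 | 2.74 | 5.5 | 19.2 | 38.3 | 82.1 |

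Nominal gaps between scheduled draws are 270 - 90 = 180 days during dosing, and 1080 - 990 = 90 days before EOS. Every tolerated lag in the table is shorter than either gap. If the transaminase peak and the bilirubin rise were caught only at successive scheduled visits, the planned rule would not count the case under these assumptions.

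**3. Share missed with follow-up sampling.** A simulation used 200,000 injuries per scenario. Assumed inputs were bilirubin >2xULN for 2 to 5 weeks, a first sample at a random time during the transaminase elevation, and retests every 7 or 14 days. The denominator is subjects with bilirubin >2xULN sampled on or within 30 days after a sampled transaminase elevation. The numerator is those among them who never show both elevations in one sample.

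| ALT/AST >3xULN lasts | Bilirubin lag | Retest every 7 days | Retest every 14 days |
|---|---|---|---|
| 3-6 weeks | 0-2 weeks | 0% | 1% |
| 3-6 weeks | 1-3 weeks | 3% | 10% |
| 3-6 weeks | 2-4 weeks | 19% | about 33% |
| 4-10 weeks | the same three lags | 0-6% across both retest intervals | (see left) |

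That makes 2 durations x 3 lags x 2 retest intervals = 12 scenarios. Ten give 10% or less. The two that exceed it combine the longest lag with the shorter elevation.

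**The case against.** The strongest reply is that little is lost. A later bilirubin rise is still counted while ALT or AST stays above 3xULN, and most assumed scenarios lose few cases or none. The lag, the durations and the retest interval are all assumptions. A 30-day window adds nothing from draws taken on their nominal scheduled days, so any gain depends on unscheduled sampling of unknown frequency. The summaries are descriptive, in a non-comparative extension. All of this stands, and it limits the weight of the point.

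The reply also notes that a missed subject may be visible elsewhere. That is right in part. The laboratory listings have no same-time rule, and one subject may appear under several parameters, but they leave out anyone whose baseline already met the threshold. Hepatic adverse events depend on reporting and coding. Neither output ties a transaminase value to a later bilirubin value.

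A reader might infer four stronger things that the documents do not support:

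- That every case with bilirubin rising after the transaminase peak is lost. The second test pattern shows otherwise.
- That one missed case turns a signal into no signal. The other liver outputs may still show that subject.
- That the SAP demands a single blood sample. It says time point and leaves the term undefined.
- That the count contradicts stopping criterion 2c in Protocol 4.4.1, "ALT or AST >3xULN and (total bilirubin >2xULN or INR >1.5". That criterion is an individual dosing rule for unexplained increases and has an INR alternative. It is silent on timing, so it cannot be read as accepting values from different dates.

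**Conclusion.** The point holds as a limited gap. Both counts omit a subject whose transaminase and bilirubin elevations do not coincide at a sampled time point, and no planned output connects the two. That follows from the SAP wording alone. The size does not: the share missed is 0% to about 33% under assumed kinetics, with 0-6% if the transaminase elevation lasts 4 to 10 weeks. The documents give no expected number of Hy's law cases, so the number missed cannot be stated. The direction is known: the planned counts can only be lower than a windowed count that contains them. This is a minor improvement, worth making because it is cheap and concerns a named AESI under a primary safety objective.

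**What to change.** In SAP 2.7.3.4:

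- Define time point, including how unscheduled samples are handled.
- Keep both planned same-time-point counts.
- Add to each summary a row for subjects with bilirubin >2xULN on or within a prespecified window after any post-baseline ALT or AST >3xULN, with ALP <2xULN at the transaminase elevation. Thirty days is a reasonable proposal, but neither document gives a figure. Every same-time-point case also meets this definition, so the new row contains the planned count.
- List each case with dated ALT, AST, bilirubin and ALP values.

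The cost is SAP wording and minor programming on data already collected, with no protocol amendment. It should be settled before database lock. The downside is that a few subjects with an unrelated later bilirubin rise will enter the new row; the dated listing lets a reader identify them.
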